### 7.3.3. Overall Survival

Overall survival is defined as the length of time from the start of the study drug (Day 1) until the date of death due to any cause. Date of death will be determined using the Death Report and the Survival Follow-Up eCRFs. Subjects who are lost-to-follow-up or still alive at the time of analysis will be right-censored at the earlier of the date the subject was last known alive and the clinical data cut-off date for the analysis. The last known alive date is defined as the later of the last study visit and the date the subject was last known alive from the Survival Follow-Up and Subject Status eCRFs.

The number of subjects who died and the number of subjects censored will be summarized. The Kaplan-Meier estimate of median OS will be presented with its 95% CI. The 95% CI will be calculated using the Brookmeyer and Crowley's method ([Brookmeyer and Crowley 1982](#)). The OS analysis will be conducted for Cohorts A-ID, A-CD, and B.

#### **7.3.4. Duration of Response**

For objective responders, DOR is the time from the first overall response contributing to an objective response as assessed by an independent centralized radiological review committee to the earlier of death or first overall response of PD occurring after the first overall response contributing to the objective response. Censoring of DOR will follow the same algorithm as the censoring of PFS (see Section 7.3.2).

The total number of responders, the number of subjects who progressed or died, and the number of subjects censored will be summarized. The Kaplan-Meier estimate of median DOR will be presented with its 95% CI. The 95% CI will be calculated using the Brookmeyer and Crowley's method (Brookmeyer and Crowley 1982). The DOR analysis will be conducted for Cohorts A-ID, A-CD, and B.

#### **7.4. Other Efficacy Analyses**

##### **7.4.1. Largest Percentage Reduction in Sum of Diameters of Target Lesions**

For subjects with measurable lesions at baseline, target lesion sizes will be measured by sum of diameters. The best percent change from baseline, defined as the largest decrease in target lesion size during the study, will also be summarized, and a waterfall plot of best percent change will be generated.

Target lesions considered "too small to measure" will be assigned a default value of 5 mm for purposes of this analysis. Likewise, target lesions identified as "not present" at postbaseline assessments will be assigned 0 mm for this analysis. In the event a target lesion is unaccounted for in a particular postbaseline timepoint (ie, the assessment is missing or NE), then the overall sum of diameters for target lesions will not be evaluable for that postbaseline timepoint.

##### **7.4.2. Investigator-Assessed Efficacy Parameters**

ORR, PFS, and DOR based on review of scans by investigator per RECIST v1.1 will be analyzed in a similar fashion as those parameters assessed by an independent centralized radiological review committee. Confirmation of CR and PR is not required.

ORR and DOR assessed by an independent centralized radiological review committee per RECIST v1.1 without requirement of CR and PR confirmation will also be analyzed.

##### **7.4.3. Eastern Cooperative Oncology Group Performance Status**

ECOG performance status and changes in status at scheduled assessment times will be summarized.

## **8. SAFETY AND TOLERABILITY**

[Appendix A](#) provides a list of data displays and sample data displays.

### **8.1. General Considerations**

The analyses for this section will be provided for the safety population. Summary tables may be replaced with listings when appropriate. For instance, an AE frequency table may be replaced with a listing if it only contains a few unique preferred terms reported on relatively few subjects.

### **8.2. Adverse Events**

#### **8.2.1. Adverse Event Definitions**

A TEAE is any AE either reported for the first time or worsening of a pre-existing event after first dose of study drug and within 30 days of last dose of study drug. Analysis of AEs (as discussed below) will be limited to TEAEs, but data listings will include all AEs regardless of their timing to study drug administration.

Adverse events will be tabulated by MedDRA preferred term and system organ class. Severity of AEs will be described and graded using the NCI CTCAE v4.03. The CTCAE reporting guidelines and grading details are available on the Cancer Therapy Evaluation Program website.

A grading (severity) scale is provided for each AE term. If the toxicity is not included in the CTCAE v4.03 criteria, it will be rated on a scale of 1 to 4 as follows: 1 = mild, 2 = moderate, 3 = severe and 4 = life-threatening. All toxicities will be graded based on the worst level reached, not the level they may have reached if they had not been treated. When the intensity of an AE changes over time for a reporting period (eg, between visits), each change in intensity will be reported as an AE until the event resolves.

The subset of AEs considered by the investigator to be related to study drug will be considered to be treatment-related AEs. The incidence of AEs and treatment-related AEs will be tabulated. Serious adverse events will also be tabulated.

Any missing onset date, causality, or severity must be queried for resolution. Unsolved missing values will be handled according to the following rules:

- An unsolved missing causality will be considered treatment related.
- An unsolved missing severity will be identified as an unknown severity.

For purposes of analysis, all AEs will be considered TEAEs unless the AE can unequivocally be defined as not treatment emergent.

#### **8.2.2. Adverse Event Summaries**

An overall summary of AEs by treatment group will include:

- Number (%) of subjects reporting any TEAEs
- Number (%) of subjects reporting any serious TEAEs
- Number (%) of subjects reporting any Grade 3 or 4 TEAEs

- Number (%) of subjects reporting any TEAEs related to INCB054828
- Number (%) of subjects who temporarily interrupted INCB054828 because of TEAEs
- Number (%) of subjects who permanently discontinued INCB054828 because of TEAEs
- Number (%) of subjects with INCB054828 dose reductions because of TEAEs
- Number (%) of subjects who had a fatal TEAE

The following summaries will be produced by MedDRA term (if  $\leq 10$  subjects appear in a table, a listing may be appropriate):

- Summary of TEAEs by system organ class and preferred term
- Summary of TEAEs by preferred term in decreasing order of frequency
- Summary of TEAEs by system organ class, preferred term, and maximum severity
- Summary of Grade 3 or higher TEAEs by system organ class and preferred term
- Summary of Grade 3 or higher TEAEs by preferred term in decreasing order of frequency
- Summary of INCB054828 treatment-related AEs by system organ class and preferred term
- Summary of treatment-related AEs by preferred term in decreasing order of frequency
- Summary of Grade 3 or higher INCB054828 treatment-related AEs by system organ class and preferred term
- Summary of TEAEs leading to death by system organ class and preferred term
- Summary of serious TEAEs by system organ class and preferred term
- Summary of treatment-related serious TEAEs by system organ class and preferred term
- Summary of TEAEs leading to INCB054828 dose interruption by system organ class and preferred term
- Summary of TEAEs leading to INCB054828 dose reduction by system organ class and preferred term
- Summary of TEAEs leading to discontinuation of INCB054828 by system organ class and preferred term
- Summary of TEAEs and Grade 3 or Higher TEAEs by preferred term in decreasing order of frequency
- Summary of treatment-emergent non-SAEs by system organ class and preferred term

## **8.3. Clinical Laboratory Tests**

### **8.3.1. Laboratory Value Definitions**

For numeric laboratory results, the change and percentage change from baseline will be calculated. Baseline will be determined according to Section 4.1.3. If there are multiple values that meet the criteria for baseline, the value from the central laboratory has priority over the value from the local laboratory. Thereafter, additional rules may be provided after consultation with the medical monitor to delineate which value will be defined as baseline.

Laboratory test values outside the normal range will be assessed for severity based on CTCAE grade or similar criteria where clinical intervention is required for CTCAE grading.

### **8.3.2. Laboratory Value Summaries**

All test results and associated normal ranges from central laboratories will be reported in SI units. All tests with numeric values will have a unique unit per test. Any laboratory test results and associated normal ranges from local laboratories will be converted to SI units.

For numeric laboratory values, baseline value, postbaseline value, change from baseline, and percent change from baseline will be summarized by visit. In addition, laboratory values and mean change from baseline will be plotted over time for selected laboratory parameters, including creatinine, parathyroid hormone, phosphate, sodium, 25-hydroxyvitamin D, and 1,25-dihydroxyvitamin D.

For the laboratory parameters that have CTCAE grading, shift tables will also be presented showing change in CTCAE severity grade from baseline to worst grade postbaseline. The denominator for the percentage calculation will be the number of subjects in the baseline category.

Categorical laboratory data will be tabulated by visit at baseline and postbaseline visits where appropriate.

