Hyperphosphatemia is an expected on-target pharmacological effect of FGFR inhibition. The incidence of hyperphosphatemia, defined as any postbaseline phosphate level exceeding 5.5 mg/dL, has been observed in the majority of subjects treated with INCB054828 (refer to the [IB](#) for complete data). Some subjects do not achieve hyperphosphatemia, and it is estimated that the pharmacological concentration of INCB054828 in these subjects is lower (see [Figure 3](#)).

Figure 3: Comparison of Steady-State Exposures for INCB054828 13.5 mg QD Between Subjects With Nonhyperphosphatemia and Hyperphosphatemia

AUC_{ss} = area under the curve at steady state; C_{min,ss} = minimum blood plasma concentration at steady state; HP = hyperphosphatemia.

The increase in serum phosphorus observed after treatment with INCB054828 was exposure-dependent and followed a sigmoid relationship. A population E_{max} model of INCB054828 AUC and maximal serum phosphate change from baseline was developed. For those subjects treated with INCB054828 13.5 mg who did not develop hyperphosphatemia, AUC for INCB054828 18 mg was estimated using a linear exposure relationship. Maximal serum phosphate change from baseline for each individual was then estimated using a population model. The maximal serum phosphate after treatment with INCB054828 18 mg was calculated by adding the baseline of serum phosphate. The simulation suggested that the serum phosphate would increase above 5.5 mg/dL after treatment with INCB054828 18 mg for the subjects treated with INCB054828 13.5 mg who did not develop hyperphosphatemia.

Therefore, up-titration of INCB054828 will be allowed to increase the dose of INCB054828 in subjects who do not achieve hyperphosphatemia when treated with 13.5 mg QD. The goal is to increase the serum concentration of INCB054828 for subjects who are assumed to have lower exposure based on a lower serum phosphate level while on treatment. Refer to Section 5.4.4 for details.

Subjects will be monitored on an ongoing basis throughout this study as per the schedules of assessments (see Table 4 and Table 5).

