3.2. Subject Exclusion Criteria

A subject who meets any of the following criteria will be excluded from the study:

1. Treatment with other investigational study drug for any indication for any reason, or receipt of anticancer medications within 28 days before first dose of study drug. Subjects must have recovered (Grade ≤ 1 or at pretreatment baseline) from AEs from previously administered therapies.
2. Untreated brain or central nervous system (CNS) metastases or brain/CNS metastases that have progressed (eg, evidence of new or enlarging brain metastasis or new neurological symptoms attributable to brain/CNS metastases). Subjects with previously treated and clinically stable brain/CNS metastases and who are off all corticosteroids for ≥ 4 weeks are eligible.
3. Known additional malignancy that is progressing or requires active treatment (ie, treatment administered within 3 years). Exceptions include basal cell carcinoma of the skin, squamous cell carcinoma of the skin, carcinoma in situ of the cervix, or other noninvasive or indolent malignancy that has undergone potentially curative therapy.
4. Are pregnant or lactating.
5. Prior receipt of a selective FGFR inhibitor.
6. Abnormal laboratory parameters:
 - a. Total bilirubin $\geq 1.5 \times$ upper limit of normal (ULN; $\geq 2.5 \times$ ULN if Gilbert syndrome or metastatic disease involving liver).
 - b. AST and ALT $> 2.5 \times$ ULN (AST and ALT $> 5 \times$ ULN in the presence of liver metastases).
 - c. Creatinine clearance ≤ 30 mL/min based on Cockcroft-Gault.
 - d. Serum phosphate $>$ institutional ULN.
 - e. Serum calcium outside of the institutional normal range or serum albumin-corrected calcium outside of the institutional normal range when serum albumin is outside of the institutional normal range.
7. History of calcium and phosphate homeostasis disorder.
8. History of human immunodeficiency virus infection.

9. Evidence of hepatitis B virus (HBV) or hepatitis C virus (HCV) active infection or risk of reactivation.
10. History or presence of an abnormal ECG that in the investigator's opinion is clinically meaningful. A screening QTcF interval > 450 milliseconds is excluded.

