8. SAFETY MONITORING AND REPORTING

8.1. Adverse Events

8.1.1. Definitions

For the purposes of this Protocol, an AE is defined as any untoward medical occurrence associated with the use of a drug in humans, whether or not considered drug related, that occurs after a subject provides informed consent. Abnormal laboratory values or test results occurring after informed consent constitute AEs only if they induce clinical signs or symptoms, are considered clinically meaningful, require therapy (eg, hematologic abnormality that requires transfusion), or require changes in the study drug(s).

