Grade 4	Life-threatening consequences; urgent intervention indicated.

Please note that a grading scale for hyperphosphatemia (elevated serum phosphate) is not in the current version of CTCAE v4.03. Grading should be applied using the table noted above ("investigations-other, specify" category in CTCAE v 4.03). Please grade the hyperphosphatemia based on clinical severity (eg, symptoms) and medical intervention measures taken (eg, binders) and not on phosphate levels.

The occurrence of AEs should be sought by nondirective questioning of the subject during the screening process after signing the ICF and at each visit during the study. Adverse events may also be detected when they are volunteered by the subject during the screening process or between visits, or through physical examination, laboratory test, or other assessments. To the extent possible, each AE should be evaluated to determine:

- The severity grade (CTCAE Grade 1 to 4).
- Whether there is at least a reasonable possibility that the AE is related to the study treatment: suspected (yes) or not suspected (no).
- The start and end dates, unless unresolved at final follow-up.
- The action taken with regard to study drug.
- The event outcome (eg, not recovered/not resolved, recovered/resolved, recovering/resolving, recovered/resolved with sequelae, fatal, unknown).
- The seriousness, as per SAE definition provided in Section 8.3.1.

Unlike routine safety assessments, SAEs are monitored continuously and have special reporting requirements (see Section 8.3.2).

All AEs should be treated appropriately. If an AE is treated with a concomitant medication or nondrug therapy, this action should be recorded on Adverse Event form and the treatment should be specified on the Prior/Concomitant Medications or Procedures and Non-Drug Therapy form in the eCRF.

Once an AE is detected, it should be followed until it has resolved or until it is judged to be permanent; assessment should be made at each visit (or more frequently if necessary) of any changes in severity, the suspected relationship to the study drug, the interventions required to treat the event, and the outcome.

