9.4.2.2. Clinical Laboratory Tests

Laboratory test values outside the normal range will be assessed for severity based on the normal ranges for the clinical reference laboratory. The incidence of abnormal laboratory values and shift tables relative to baseline will be tabulated.

Laboratory data will be classified into Grades 1 through 4 using CTCAE v4.03. The following summaries will be produced for the laboratory data:

- Number and percentage of subjects with worst postbaseline CTCAE grade (regardless of baseline value). Each subject will be counted only for the worst grade observed postbaseline.
- Shift tables from baseline to the worst postbaseline value using CTCAE grade.
- For laboratory parameters where CTCAE grades are not defined, shift tables to the worst postbaseline value using the low/normal/high classifications based on laboratory reference ranges.

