| 3.3.2             | Shift Summary of Hematology Values in CTC Grade - To the Worst Abnormal Value   | Safety            |
| 3.3.3             | Summary of Treatment-Emergent Worsening of Laboratory Abnormalities - Hematology  |                   |
| 3.3.4             | Summary of Laboratory Values - Chemistry  | Safety            |
| 3.3.5             | Shift Summary of Chemistry Values in CTC Grade - To the Worst Abnormal Value  | Safety            |
| 3.3.6             | Summary of Treatment-Emergent Worsening of Laboratory Abnormalities - Chemistry   |                   |
| 3.3.7             | Summary of Laboratory Values - Coagulation  | Safety            |
| 3.3.8             | Shift Summary of Coagulation Values in CTC Grade - To the Worst Abnormal Value  | Safety            |
| 3.3.9             | Summary of Treatment-Emergent Worsening of Laboratory Abnormalities - Coagulation   | Safety            |
| 3.3.10            | Summary of Laboratory Values - Urinalysis   | Safety            |

| Table No.   | Title   | Population |
|--------------------|--|-------------------|
| Vital Signs |  |                   |
| 3.4.1              | Summary of Systolic Blood Pressure                                 | Safety            |
| 3.4.2              | Summary of Diastolic Blood Pressure                                | Safety            |
| 3.4.3              | Summary of Pulse   | Safety            |
| 3.4.4              | Summary of Body Temperature  | Safety            |
| 3.4.5              | Summary of Respiratory Rate  | Safety            |
| 3.4.6              | Summary of Body Weight   | Safety            |
| ECG         |  |                   |
| 3.5.1              | Summary of PR Interval (ms) From 12-Lead ECG                       | Safety            |
| 3.5.2              | Summary of QRS Interval (ms) From 12-Lead ECG                      | Safety            |
| 3.5.3              | Summary of QT Interval (ms) From 12-Lead ECG                       | Safety            |
| 3.5.4              | Summary of QTc Interval (ms) From 12-Lead ECG                      | Safety            |
| 3.5.5              | Summary of Heart Rate (bpm) From 12-Lead ECG                       | Safety            |
| 3.5.6              | Summary of Outliers of QT and QTc Interval Values From 12-Lead ECG | Safety            |

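### The SAP drops the protocol's low/normal/high shift tables for ungraded laboratory tests, so high phosphate has none, and moves the notable QTcF limit from 450 to 460 ms, while declaring no changes

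*SAP*

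**What the plan says.** **Laboratory shift tables.** Protocol Section 9.4.2.2 lists three laboratory summaries: worst postbaseline CTCAE grade, shift tables by CTCAE grade, and, for everything else, "For laboratory parameters where CTCAE grades are not defined, shift tables to the worst postbaseline value using the low/normal/high classifications". SAP Section 8.3.2 keeps the graded kind only: "For the laboratory parameters that have CTCAE grading, shift tables will also be presented showing change in CTCAE severity grade". In SAP Appendix A the chemistry entry is Table 3.3.5, "Shift Summary of Chemistry Values in CTC Grade - To the Worst Abnormal Value". Hematology (3.3.2) and coagulation (3.3.8) have titles of the same form.

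**Phosphate.** Protocol Section 8.1.2 says that "a grading scale for hyperphosphatemia (elevated serum phosphate) is not in the current version of CTCAE v4.03". It tells sites to grade the adverse event by symptoms and intervention rather than by the phosphate value. Protocol Section 1.3.2.1, by contrast, treats hyperphosphatemia as a laboratory event, "defined as any postbaseline phosphate level exceeding 5.5 mg/dL".

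**ECG limits.** Protocol Table 10 sets the high QTcF limit for a clinically notable value at > 450 ms; SAP Table 3 sets it at > 460 ms. Protocol Table 10 has an RR row (> 1330 or < 600 ms) and SAP Table 3 has none. The low QTcF limit and all PR, QRS and QT limits agree.

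**Declaration.** SAP Section 10.1, which should record departures from the protocol's analyses, is marked as not applicable. The change list in SAP Section 10.2.1 mentions neither point.

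**The concern.** Protocol Section 5.4.3 calls high phosphate an expected on-target effect, and the protocol uses phosphate level to guide interruption, dose reduction and up-titration. It is also the parameter for which the omitted table would be most informative. Exclusion criterion 6d bars subjects whose serum phosphate is above the institutional upper limit, so nearly every subject whose worst value is high would have moved there on treatment. Without the table, no prespecified output counts subjects by worst phosphate category.

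For QTcF, exclusion criterion 10 bars a screening value above 450 ms, the same number as the protocol's notable limit. Under the protocol, a subject who rises from an eligible value to between 450 and 460 ms is listed as notable. Under the SAP that subject is not.

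Both differences change what the safety report shows, and a reader of SAP Section 10.1 would conclude that there are none.

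**Working it through.** The plan gives no figure to reproduce on this point. The check is a comparison of text, followed by a few small calculations to judge size.

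**1. Shift tables, side by side**

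| Parameter type | Protocol 9.4.2.2 | SAP 8.3.2 and Appendix A |
|---|---|---|
| CTCAE grade exists | Shift by grade, baseline to worst | Shift by grade, baseline to worst |
| No CTCAE grade | Low/normal/high shift to worst | None |

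Of the three shift tables in Appendix A, 3 are in CTC grade and 0 cover ungraded parameters. High phosphate is ungraded by the protocol's own statement, so it falls in the empty cell.

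**2. Do other outputs fill the gap?**

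- By-visit summaries and the plot of mean change (SAP 8.3.2) describe values at nominal visits. They do not count subjects by worst value.
- Categorical tabulation (SAP 8.3.2) is also by visit.
- The abnormal chemistry listing (2.8.2.2) shows data but summarises nothing.
- Table 3.3.6, "Summary of Treatment-Emergent Worsening of Laboratory Abnormalities - Chemistry", might count subjects, but the SAP does not say what classification defines worsening.
- Adverse event tables give incidence but are a partial substitute. Under Protocol Section 8.1.1, laboratory abnormalities "constitute AEs only if they induce clinical signs or symptoms, are considered clinically meaningful, require therapy" or lead to a change in study drug. For > 5.5 to 7 mg/dL, Protocol Table 3 lists only a low-phosphate diet and no action on drug, so some of these values may not be recorded as adverse events.

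**3. How common is the parameter?** Protocol Table 1 gives phase 1 treatment-emergent adverse event counts. With exact (Clopper-Pearson) 95% limits:

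- All regimens: 74/105 = 70.5% (60.8 to 79.0).
- 13.5 mg continuous: 14/15 = 93.3% (68.1 to 99.8).

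These are adverse event counts. They show that the parameter matters, but they do not measure how many laboratory shifts would go unreported.

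**4. QTcF.** The limits differ by 460 − 450 = 10 ms. The documents do not say how many subjects will have a worst value in that band. If it were 1% to 10% of the 240 planned subjects (an assumption with no source in the documents), the number would be 0.01 × 240 = 2.4 to 0.10 × 240 = 24.

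**5. RR.** Converting to heart rate, 60000/1330 = 45.1 bpm and 60000/600 = 100 bpm. These match the pulse limits in SAP Table 2 (< 45 and > 100 bpm), so losing the RR row matters little.

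**6. Version.** SAP Section 2.1 bases the SAP on Protocol Amendment 6 and keeps it in force for later amendments. The protocol in hand is Amendment 7. Its change list names nothing in Section 9.4.2, though it allows for unlisted administrative changes.

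**The case against.** The best counter-argument on phosphate is SAP Section 8.3.1, which grades out-of-range values by CTCAE or by similar criteria where CTCAE grading depends on clinical intervention. Since sites grade hyperphosphatemia by intervention, one could argue that phosphate reaches Table 3.3.5 or 3.3.6 by that route. But the wording concerns parameters whose CTCAE grade itself depends on intervention. It does not create a scale for a parameter that has none, and it does not restore a low/normal/high table.

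Second, the introduction to Appendix A calls its lists guidelines and refers to standard tables that are not available here, so the contents of Tables 3.3.6 and 3.5.6 cannot be judged from their titles. That is fair for those two tables. It does not help with the shift tables, because the restriction to graded parameters is in the body of Section 8.3.2.

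Third, the omitted table would classify by laboratory reference range, not by 5.5 mg/dL or the bands of Protocol Table 3. This stands: a banded phosphate table was never planned and can only be a suggestion.

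Fourth, phase 1 shows that hyperphosphatemia is often captured as an adverse event, all analyses are exploratory (SAP Section 3.1), every ECG value is still listed (2.10.1), a QT/QTc outlier table (3.5.6) is planned without stated limits, and the QTcF discontinuation criterion in Protocol Section 5.4.5 is unaffected. All of this is true and limits the consequence. It does not reconcile the two documents.

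Finally, without the Amendment 6 text one cannot be certain that Section 10.1 was wrong when written. That caveat stands too, but the SAP governs under Amendment 7, and the two documents now disagree.

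**Conclusion.** The concern holds. Following the SAP as written would omit a protocol-specified safety table that covers the drug's expected on-target effect, and would leave QTcF values above 450 and up to 460 ms out of the notable listing. Neither difference is declared.

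The loss is of summaries, not of data. For phosphate it is the count of subjects moving from normal to high at worst value. For QTcF the number affected is unknown; 2 to 24 is an illustration resting on an assumed 1% to 10%. The RR omission is minor. The primary ORR analysis is not affected. The documents do not show which QTcF limit is intended, and no view is taken here.

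**What to change.** 1. In SAP Section 8.3.2 and Appendix A, restore low/normal/high shift tables to the worst postbaseline value for parameters without a CTCAE grade, naming high phosphate explicitly.
2. State the classification used in Table 3.3.6.
3. Reconcile the QTcF limit and the RR row between Protocol Table 10 and SAP Table 3.
4. Record any difference that remains, with its reason, in SAP Section 10.1.

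Optionally, tabulate worst phosphate by cohort in the bands that Protocol Table 3 already uses (≤ 5.5, > 5.5 to 7, > 7 to 10, > 10 mg/dL). This would go beyond what the protocol plans.

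The cost is one or two tables from data already collected, one reconciled threshold and a short entry in Section 10.1. No new data are needed and no efficacy analysis changes.
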